8.8 Conventional Physiotherapy tracking

Patients on the conventional physiotherapy arm will need to keep track of the quantity and type of physical rehabilitation they receive, as described in Appendix F. They can request help from their physiotherapist. Patients will need to bring their diaries to the site visits so the data can be registered in the database.

8.9 Safety Assessments

Adverse events of special interest, serious adverse events and all device related non-serious and serious adverse events will be collected from the signature of the ICF until the participation of the patient is completed within the study. Serious Adverse Device Effects will be reported to the authorities.

In case an adverse event is suspected during the regular follow-up calls between the patient and the APA specialist, the APA specialist will contact the Investigator to enquire the investigation of the event and the assessment of severity and causality.

Detailed instructions on recording and reporting of serious safety incidents will be provided in the Study Procedure Manual.

8.9.1 Adverse Events

An Adverse Event (AE) is "any untoward medical occurrence in a patient or clinical investigation participant administered a pharmaceutical product and which does not necessarily have a causal relationship with this treatment". Since no pharmaceutical products will be administered in this study no AEs will be collected other than the AEs of Special Interest (Section 8.7.3).

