	Change from baseline to Week 12 (Visit 3) in Stance Time Variability assessed during the 6MWT.
	Secondary Endpoints
	• Rate of falls at Week 12 based on the results of the falls diary.
	• Change from baseline to Week 12 (Visit 3) in the asymmetry of the swing duration assessed during the 6MWT.
	• Change from baseline to Week 12 (Visit 3) in the Mini-BESTest.
	• Change from baseline to Week 12 (Visit 3) in Unified Parkinson's Disease Rating Scale (MDS-UPDRS) Part III sub-score.
	• Change from baseline to Week 12 (Visit 3) in the results of the Parkinson Disease Questionnaire (PDQ-39).
	Exploratory Endpoints
	• Rate of falls at Week 24 based on the results of the falls diary.
	• Change from Baseline to Week 24 (Visit 4) and from Week 12 (Visit 3) to Week 24 in:
	- Gait velocity (cm/s) assessed during the 6MWT
	- Stance Time Variability assessed during the 6MWT
	- Asymmetry of the swing duration assessed during 6MWT
	- the Mini-BESTest
	- MDS-UPDRS Part III sub-score
	- the results of the PDQ-39
	 Change from Baseline to Week 12 (Visit 3) and to Week 24 (Visit 4) and from Week 12 to Week 24 in the:
	- gait parameters measured by the FeetMe Monitor during the 6MWTs other than ones of the primary and secondary endpoints
	- gait parameters measured by the FeetMe Monitor during remote gait monitoring
	- results of the pain VAS
	- results of the Parkinson Disease Sleep Scale 2 (PDSS2)
	- results of the Clinical and Patient Global Impression of Severity scales (CGI/PGI-S)
	- results of the Clinical and Patient Global Impression of Improvement scales (CGI/PGI-I)
	• results of the MDS-UPDRS I, II and IV sub scores
	• Actual versus prescribed time spent on physiotherapy at Week 12 and Week 24.
· · · · · · · · · · · · · · · · · · ·	

	• Results of the Patient and Investigator satisfaction questionnaire.
	• Number of device and protocol procedure related adverse events at Week 12 and at Week 24.

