8.9.2 Serious Adverse Events (SAE)

An SAE is an adverse event that could lead to any of the following:

CIP Number 2023-A00150-45 Final version 0.2

a) Death

- b) Serious deterioration in the health of the patient, users, or other persons as defined by one or more of the following:
 - 1) a life-threatening illness or injury
 - 2) a permanent impairment of a body structure or a body function including chronic diseases
 - 3) in-patient hospitalisation or prolonged hospitalisation
 - 4) medical or surgical intervention to prevent life-threatening illness or injury, or permanent impairment to a body structure or a body function.

c) Foetal distress, foetal death, a congenital abnormality, or birth defect including physical or mental impairment.

Serious Adverse Events will be collected and reported as described in the Study Procedure Manual.

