8.9.3 AEs of Special Interest

Given the objective of the study and the disease assessed, AEs of special interest will be collected irrespective of seriousness and relatedness. These AEs are typically ones concerning the motor functions of the patients and include but are not limited to falls, freezing of gait, rigidity, bradykinesia, dyskinesia, dizziness, stiffness, vertigo and in general the worsening of the disease.

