8.9.4 Adverse Device Effect (ADE)

An ADE is an adverse event related to the use of an investigational medical device. This definition includes adverse events resulting from; insufficient or inadequate instructions for use, deployment, implantation, installation, or operation, or any malfunction of the investigational medical device. It also covers any event resulting from use error or from intentional misuse of the investigational medical device.

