9.2.7 Analysis of safety outcomes

The SAF will be used to perform all safety analyses.

If not otherwise stated, only device-related safety data will be considered in tables and figures. All safety data will be included in listings, with flags for safety data not considered to be treatment emergent.

Device-related AEs and SAEs will be tabulated by patient cohorts, SOC, and preferred terms. The events will also be summarized by maximum intensity, relationship to study treatment and outcome (premature discontinuation from treatment).

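### Section 8.9.1 limits adverse event collection to AEs of special interest, against 8.9, 8.9.2 and 8.5, and no section clearly collects the non-serious procedure-related events that the safety endpoint counts

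*Protocol*

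**What the plan says.** Section 8.9 of the protocol sets the scope of safety collection from consent until the patient's participation ends: "Adverse events of special interest, serious adverse events and all device related non-serious and serious adverse events will be collected". Its first subsection, 8.9.1, takes its AE definition from drug trials, tying an event to the administration of a pharmaceutical product. It then concludes: "Since no pharmaceutical products will be administered in this study no AEs will be collected other than the AEs of Special Interest". For AESIs it refers to section 8.7.3, which is 8.9.3 in this version.

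The neighbouring sections read as follows.

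- 8.9.2: "Serious Adverse Events will be collected and reported as described in the Study Procedure Manual".
- 8.9.3, on AESIs, which are collected whatever their seriousness or relatedness: "These AEs are typically ones concerning the motor functions of the patients and include but are not limited to falls, freezing of gait".
- 8.9.4: "An ADE is an adverse event related to the use of an investigational medical device".
- 8.5: a device deficiency that leads to a safety event has to be recorded as an AE, with its relatedness.
- 8.9.6: the investigator assesses causality against an investigational medicinal product (IMP).

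Two places use these data. The synopsis lists the exploratory endpoint "Number of device and protocol procedure related adverse events at Week 12 and at Week 24", and Table 5.1 has the same endpoint in slightly different words. Section 9.2.7 plans the display: "Device-related AEs and SAEs will be tabulated by patient cohorts, SOC, and preferred terms".

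**The concern.** Two adjacent sections give investigators different rules on what to record. Section 8.9.1 carries the heading Adverse Events, states a categorical rule and gives a reason for it, so a site could follow it in good faith. Another site could follow 8.9 with equal justification. The count of related AEs would then depend partly on which section each of the six centres applied.

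The error runs in one direction. Events left unrecorded lower the count and make the device look safer. Section 4.6 already notes that no device-related AEs have been reported with the insoles, so a low count in this trial could be taken as confirmation. The endpoint is the only one attached to the safety objective in Table 5.1.

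**Working it through.** There is no figure in the plan to reproduce. The check sets each type of event against the two collection rules and against what the endpoint and 9.2.7 need.

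| Event type | Under 8.9 | Under 8.9.1, literally | Needed by |
|---|---|---|---|
| AESI, any seriousness or relatedness | collected | collected | endpoint, if device- or procedure-related; 9.2.7, if device-related |
| SAE that is not an AESI | collected | excluded (but 8.9.2 collects it) | endpoint, if device- or procedure-related; 9.2.7, if device-related |
| Non-serious, device-related, not an AESI | collected | excluded | endpoint and 9.2.7 |
| Non-serious, related to a study procedure but not to the device, not an AESI | not named | excluded | endpoint |
| Non-serious, unrelated, not an AESI | not collected | not collected | neither |

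1. **Row 3 is the direct contradiction.** A skin lesion under an insole is an adverse device effect under 8.9.4. It is recorded under 8.9 and left out under 8.9.1. If it is left out, it is missing from both the endpoint and the 9.2.7 table.

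2. **Row 2 shows that 8.9.1 cannot stand as written.** Its sentence excepts only AESIs, so it excludes SAEs, against 8.9 and 8.9.2. It also conflicts with 8.5, which requires an AE record for a deficiency that causes a safety event, with no restriction to AESIs.

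3. **Row 4 is a gap in both rules.** Section 8.9 names only device-related events among the non-serious ones. Section 8.9.5 provides for recording serious incidents related to the device or a study procedure, but nothing equivalent exists for non-serious procedure-related events. Section 8.9.6 has no causality category for a procedure, because it asks only about an IMP. Deleting the sentence in 8.9.1 would repair rows 2 and 3 but not row 4.

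4. **The definition feeds into others.** Sections 8.9.2 and 8.9.4 define SAEs and adverse device effects as adverse events that meet a further condition, so both inherit the drug-based definition in 8.9.1. Patients do take their own Parkinson's medication. The difficulty is that, as 8.9.1 itself says, the study gives no pharmaceutical product.

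5. **Size.** The one related figure is in section 4.6: about 2530 users of the current insoles and no device-related AEs reported. At face value the rule of three gives an upper bound of 3 / 2530 = 0.12%, or 150 × 0.0012 = 0.2 events among 150 patients. That figure does not say how events were sought and concerns the insoles, not study procedures. By contrast, an assumed rate of 2% to 10% would give 150 × 0.02 = 3 to 150 × 0.10 = 15 events, but nothing in the protocol supports those rates. The answer depends entirely on the assumption, so no size can be derived.

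**The case against.** The best reply is that nobody would read 8.9.1 so strictly. Section 8.9 governs its subsections, SAEs and adverse device effects have subsections of their own, and 9.2.7 expects device-related AEs in its table. On that view 8.9.1 only switches off routine events that are non-serious and unrelated (the last row of the table). This is probably what the authors meant. It does not remove the problem, because the sentence makes a single exception and sites work from the text. Nor does it help the procedure-related events, which 8.9 does not name either.

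The rest of the objection limits how far the point goes, and it stands.

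- A reader might infer that sites following 8.9.1 would report almost no non-motor device events and that the missing events could never be recovered. The documents do not support this. Potential adverse events are asked about at Visit 3, Visit 4 and the End of Study Visit. The follow-up calls by the adapted physical activity specialist also document them, and suspected events are passed to the investigator. In addition, the AESI list is open-ended.
- A charger fault is not an example of a lost event. It is a device deficiency under 8.5, and if it caused harm it would have to be recorded as an AE.
- Injuries from app-guided exercises in the FeetMe arm do not clearly fall outside 8.9. Section 4.3 describes the application under the investigational device, so such an injury can plausibly be an adverse device effect.
- A demand to collect all exercise-related AEs in both arms would go beyond the endpoint, which names device- and procedure-related events. It would also reach into the control care that section 4.5 deliberately leaves unstandardised.

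**Conclusion.** The contradiction is real, and 8.9.1 is wrong as written. Followed literally, it leaves non-serious device-related events that are not AESIs uncollected and conflicts with 8.9, 8.9.2 and 8.5. Separately, non-serious, non-AESI procedure-related events have no clear collection rule in 8.9 or 8.9.1, although the endpoint counts them.

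The consequence is a possible undercount of one exploratory endpoint and, for device-related events, of the 9.2.7 table. It depends on sites following 8.9.1. A reader might want to attach a number of lost events, but the protocol gives no rate from which to derive one. Motor and fall-type events are captured as AESIs under either section. The primary, key secondary and other efficacy analyses are not touched. The point deserves correction because the stated rule conflicts with the endpoint it is meant to serve and the repair is cheap.

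**What to change.** 1. In 8.9.1, replace the drug-based definition with a device-study one: any untoward medical occurrence in a participant, whether or not related to the device. Correct the cross-reference to 8.9.3.
2. Delete the sentence in 8.9.1 that restricts collection to AESIs.
3. State one scope, in identical terms, in 8.9 and 8.9.1: AESIs, SAEs, and all device-related and protocol-procedure-related AEs, serious or not, from signature of the consent form to the end of participation.
4. In 8.9.6, assess causality against the device and the study procedures in place of an IMP.

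The cost is protocol wording, matching eCRF completion guidance and a few extra AE entries. Routine non-serious, unrelated events outside the AESI category would remain uncollected, as now.

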8.9.6 Assessment Definitions

Assessment of Intensity

The investigator must assess the intensity of the safety event using the following definitions:

- Mild the event causes minimal discomfort and does not interfere in a significant manner with the patient's normal activities.
- Moderate the event is sufficiently uncomfortable to produce some impairment of the patient's normal activities.
- Severe the event is incapacitating, preventing the patient from participating in the patient's normal activities.

Assessment of Causal Relationship

The investigator must assess the causal relationship between the adverse event and the Investigational Medicinal Product (IMP) using the following definitions:

- Probable – the event has a strong temporal relationship to the IMP or recurs on rechallenge, and another aetiology is unlikely or significantly less likely.

- Possible the event has a suggestive temporal relationship to the IMP, and an alternative aetiology is equally or less likely.
- Not related the event has no temporal relationship to the IMP or is due to an underlying/concurrent disorder or effect of another drug (that is, there is no causal relationship between the IMP and the adverse event).

An event is considered causally related to the use of the IMP when the causality assessment is probable or possible.

Assessment of Outcome

The investigator must assess the outcome of an event using the following definitions:

- Recovered the patient has recovered completely, and no symptoms remain.
- Recovering the patient's condition is improving, but symptoms remain.
- Recovered with sequelae the patient has recovered, but some symptoms remain (for example, the patient had a stroke and is functioning normally, but has some motor impairment).
- Not recovered the patient's condition has not improved, and the symptoms are unchanged
- Death

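### Section 8.9.1 restricts adverse event collection to events of special interest, contradicting 8.9, 8.9.2 and 8.5; the safety endpoint also counts non-serious procedure-related events that no section collects.

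*Protocol*

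**What the plan says.** Section 8.9 sets the collection rule for the study: "Adverse events of special interest, serious adverse events and all device related non-serious and serious adverse events will be collected", from consent to the end of the patient's participation.

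Section 8.9.1 then defines an adverse event in terms of a participant given a pharmaceutical product. It reasons that none is given here and concludes that "no AEs will be collected other than the AEs of Special Interest".

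The neighbouring sections do not follow that restriction:

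- Section 8.9.2: "Serious Adverse Events will be collected and reported as described in the Study Procedure Manual".
- Section 8.9.3, on events of special interest: "These AEs are typically ones concerning the motor functions of the patients and include but are not limited to falls". They are collected whatever their seriousness or relatedness.
- Section 8.9.4: "An ADE is an adverse event related to the use of an investigational medical device". This is a definition. It gives no collection rule of its own.
- Section 8.5 requires a device deficiency that leads to a safety event to be recorded as an adverse event, with its relatedness.
- Section 8.9.5 has serious incidents related to the device or to a study procedure entered in the eCRF.
- Section 8.9.6 has investigators grade causality against an investigational medicinal product. Its categories refer to rechallenge and to the effect of another drug.

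The synopsis lists as an exploratory endpoint the "Number of device and protocol procedure related adverse events at Week 12 and at Week 24", and Table 5.1 carries the same endpoint. Section 9.2.7 tabulates device-related adverse events and serious adverse events by system organ class and preferred term.

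**The concern.** Sections 8.9 and 8.9.1 are both collection rules, they cover the same events, and they disagree. Under 8.9.4 a device effect is an adverse event, so the exclusion in 8.9.1 reaches every device effect that is not of special interest, and the sentence makes no exception for them. The reason it gives is a drug-trial reason that does not fit a device investigation.

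At stake is the study's only safety endpoint, a count of device- and procedure-related events. An event that was never recorded cannot be recovered at the analysis stage. If sites read the sections differently, the count would partly reflect which section each site followed, and a low count would be hard to interpret. Section 4.6 rests part of the benefit-risk case on no device-related events having been reported so far, and section 10.1 plans no data monitoring committee.

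**Working it through.** The protocol states no expected number or rate of adverse events, so there is no figure to reproduce. The check sorts events into classes and reads off what each section does with them.

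| Class of event | 8.9 | 8.9.1 as worded | Other sections | Counted in the endpoint? |
|---|---|---|---|---|
| (a) Special interest | Collected | Collected | 8.9.3: collected | If device- or procedure-related |
| (b) Serious, not special interest | Collected | Not collected | 8.9.2: collected | If device- or procedure-related |
| (c) Non-serious, device-related, not special interest | Collected | Not collected | 8.5: only if it arises from a device deficiency; 8.9.4: definition only | Yes |
| (d) Non-serious, procedure-related only, not special interest | Not listed | Not collected | None | Yes |
| (e) Non-serious, unrelated, not special interest | Not listed | Not collected | None | No |

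Reading the rows:

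1. **Classes (b) and (c) show the contradiction.** Section 8.9 collects both and 8.9.1 excludes both. Section 8.9.2 rescues class (b). Class (c) has only the partial cover of 8.5, yet it is counted in the endpoint and tabulated under 9.2.7. Skin irritation from the insoles, not caused by a deficiency, would be one such event (my illustration, not the protocol's).
2. **Class (d) is a separate gap.** Neither 8.9 nor 8.9.1 collects it, so deleting the sentence in 8.9.1 would not close it. Section 8.9.5 covers procedure-relatedness for serious incidents only, and 8.9.6 has no procedure-relatedness rating.
3. **Class (e) is the only class outside special interest on which 8.9 and 8.9.1 agree and which the endpoint does not need.** If 8.9.1 was meant to drop only this class, the sentence is redundant, because 8.9 already leaves it out.
4. **The definition in 8.9.1 causes a further difficulty.** Taken literally, no event in this trial is an adverse event, since no pharmaceutical product is given. The serious event and device effect definitions build on that term.

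**The case against.** The strongest reply is that 8.9 is the parent section and is explicit: "all device related non-serious and serious adverse events will be collected from the signature of the ICF". Sections 8.9.2, 8.9.4, 8.5 and 9.2.7 are consistent with it. Section 4.4 has potential adverse events recorded from each follow-up call in the FeetMe arm, and sections 7.4.3, 7.5.3 and 7.6 ask about them at visits. On this reading 8.9.1 drops only general, unrelated, non-serious events. That may well be the intention. It does not settle the matter, because the sentence does not say so, and asking about events does not decide which are recorded.

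Three stronger readings are tempting, and the protocol does not support them.

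- A reader might infer that the endpoint will be undercounted. That happens only where a site follows 8.9.1 against its parent section.
- A reader might infer that only motor events would be collected under 8.9.1. Section 8.9.3 calls the events of special interest typically motor and leaves the list open; it includes dizziness, vertigo and general worsening of the disease. The gap is narrower than a purely motor list would leave.
- A reader might infer that relation to study procedures is never assessed and that this part of the endpoint cannot be derived at all. Section 8.9.5 recognises it for serious incidents. What is missing is collection of the non-serious events outside special interest, and a defined rating.

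It is also fair to say that the medicinal-product wording in 8.9.6 looks carried over from a drug protocol, and that 8.9.4 and 8.9.5 already tie relatedness to the device. By itself that is an editorial matter. The missing procedure rating is not.

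**Conclusion.** The point stands as an internal contradiction, with a separate mismatch between endpoint and collection. Section 8.9.1 conflicts with 8.9, 8.9.2 and 8.5, and a site following it may fail to record non-serious device-related events outside the special-interest list. Independently, non-serious procedure-related events are counted in the endpoint without a collection rule or a relatedness rating.

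The size of any under-collection cannot be estimated: the protocol gives no event rates, and the loss depends on how sites resolve the conflict. The Study Procedure Manual is not available here; the protocol cites it for serious events, so it cannot be assumed to settle the non-serious ones. The endpoint is exploratory and safety is only tabulated and listed, so the efficacy conclusions are untouched. The correction should still be made, because it determines which safety data are collected.

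**What to change.** - In 8.9 and 8.9.1, state one list of collected classes that matches the endpoint: events of special interest, all serious adverse events, and all device-related and procedure-related adverse events, serious or not. Remove the conflicting exclusion.
- Replace the pharmaceutical-product definition of an adverse event with one suited to a device investigation.
- In 8.9.6, rate relation to the investigational device and, separately, relation to study procedures, in place of relation to a medicinal product.
- Correct the cross-references while editing: 8.9.1 points to 8.7.3 for events of special interest, which are in 8.9.3, and 8.9.5 points to 8.7.2 for serious events, which are in 8.9.2.

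The cost is minor protocol wording and one added eCRF field for procedure-relatedness. The eCRF is not shown, so that field may already exist.
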